## 9.6. Data Management

An eCRF will be created in a commercial electronic data capture system to collect the data listed in the Variables (Section 9.3) section of the protocol. Personal identifying data such as names and social security numbers will not be collected. The study CRF will be archived in the study Trial Master File (TMF).

After training in the use of the electronic data capture tool and assignment of a unique log-in and password, site staff will enter relevant data into the eCRF. The data will be stored in secure network drives with access for authorized personnel only. Investigators will electronically sign the eCRFs to confirm responsibility for the data.

## 9.7. Data Analysis

Categorical variables will be summarized descriptively by number and percentage of patients in each categorical definition including 95% confidence intervals. Continuous variables will be summarized descriptively by mean, standard deviation, median, lower quartile, upper quartile, minimum and maximum.

Multivariate Poisson regression analyses will be used to estimate rates of ADRs and SADR, adjusted for potential confounders (demographics, baseline disease assessment, medical history, treatment history, treatment changes; see section 9.3).

Multivariate Cox Proportional Hazard analyses will be used to model time-to-event data, and time to ADRs, SADR and AESIs.

Kaplan Meier curves will be used to illustrate time-to-event analyses.

Special focus will be given to the differences in retrospective and prospective data collection. Although not by intention, data might be collected differently in retrospect compared to patient's data that will be collected prospectively. Retrospective patients will be recruited through systematic search of the sites' patient data management system, whereas prospective data will be collected from those patients prescribed idelalisib after the start of the study. Behavioral changes of the site staff after the initiation of the study might play a role in differential data collection. Thus, missing data for the retrospective data might be an issue. Stratified analyses will be conducted to account for this potential bias.

The extent of missing data in the study will be described and tabulated. Imputation methods will be used to account for missing values in the dataset for those variables used in multivariate modeling (demographics, baseline disease assessment, medical history, treatment history) and changes in idelalisib treatment following the current ENCePP guidelines (Methodological Standards in Pharmacoepidemiology: Section 5.3. Handling of missing data;

[http://www.encepp.eu/standards\\_and\\_guidances/methodologicalGuide5\\_3.shtml](http://www.encepp.eu/standards_and_guidances/methodologicalGuide5_3.shtml) {Rubin 1987}, {Moons 2006}, {Welch 2014}. Multiple imputation by chained equations (MICE) as sequential regression multiple imputation will be used handling of missing data {Azur 2011}. Using MICE, missing values are imputed based on the observed values for a given individual and the relationships within the data for other participants.

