**Study Size:**

This study aims to include patients who have been or are currently being treated with idelalisib according to the product information and treatment guidelines in routine clinical practice for the treatment of refractory FL, after marketing authorisation in the EU (September 2014) and Australia (January 2015).

Assuming a median treatment period of 8 months, a retrospective timeframe of around 3 years and a prospective observation period of 2.5 years, it is expected that data of approximately 300 patient-years will be collected.

Patients will be identified and enrolled in Europe (pending outcome of study feasibility: Australia, Austria, Belgium, France, Germany, Greece, Ireland, Italy, Portugal, Spain, Sweden, Switzerland and the United Kingdom) and Australia.

---

**Data Analysis:** Continuous variables will be summarized by mean, standard deviation, median, lower quartile, upper quartile, minimum and maximum. Categorical variables will be summarized by number and percentage of patients in each categorical definition including 95% confidence intervals.

Multivariate Poisson regression analyses will be used to estimate adjusted rates of ADRs and SADR.

Multivariate Cox Proportional Hazard analyses will be used to model time-to-event data, and time to ADRs and SADR.

Kaplan Meier will be used to illustrate time-to-event analyses.

Stratified analyses will be used to account for potential behavioral changes of the site staff after the initiation of the study that might introduce bias between retrospective and prospective data collection.

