## **8. RESEARCH QUESTIONS AND OBJECTIVES**

The primary objective of this study is:

To assess the overall safety profile of idelalisib monotherapy in patients with refractory FL.

Serious Adverse Events (SAEs) will be collected and according rates will be estimated. Focus will be given to special health outcomes of interest (HOIs) such as transaminase elevation, severe diarrhoea/colitis, pneumonitis, neutropenia, rash, Stevens-Johnson syndrome – Toxic epidermal necrolysis (SJS-TEN) and serious infections (including opportunistic infections such as *Pneumocystis jirovecii* pneumonia [PJP]) and cytomegalovirus [CMV] as listed in the Zydelig Risk Management Plan (RMP) for the EU (Version 2.0).

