#### **11.3.5. Serious Adverse Drug Reaction**

A serious adverse drug reaction (SADR) is defined as any SAE that is considered causally related to the medicinal product at any dose administered.

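### The objective promises SAE rates with a focus on HOIs, but the only rate model named covers ADRs and SADRs, and the Cox sentence in 9.7 adds an undefined term, AESIs

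*Protocol*

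**What the plan says.** **Objective.** Protocol section 8 states "Serious Adverse Events (SAEs) will be collected and according rates will be estimated" and continues "Focus will be given to special health outcomes of interest (HOIs) such as transaminase elevation, severe diarrhoea/colitis, pneumonitis, neutropenia, rash", followed by further events. The synopsis carries the same text. Neither place makes relatedness to idelalisib a condition.

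**Rate analysis.** Section 9.7 states "Multivariate Poisson regression analyses will be used to estimate rates of ADRs and SADR, adjusted for potential confounders". The synopsis, under Data Analysis, states "Multivariate Poisson regression analyses will be used to estimate adjusted rates of ADRs and SADR". No other rate model is named.

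**Time-to-event analysis.** Section 9.7 states "Multivariate Cox Proportional Hazard analyses will be used to model time-to-event data, and time to ADRs, SADR and AESIs". The synopsis uses the Cox model "to model time-to-event data, and time to ADRs and SADR", without AESIs.

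**Definitions.** Section 11.3.5 defines an SADR as "any SAE that is considered causally related to the medicinal product". Section 11.3.4 also makes causal relationship part of the definition of an ADR, but without requiring seriousness. Under section 11.5 the investigator or a qualified sub-investigator decides yes or no for each event. The glossary lists HOI but not AESI, and section 9.3 lists the HOIs.

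**The concern.** The study has no comparator, so the absolute event rate is its main product. According to section 7.1, it was requested after an increased risk of death and a higher incidence of SAEs, mostly infections, in other idelalisib trials. The objective answers that request with SAE rates. The analysis section then names outcomes that have first passed through a causality judgement.

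An analysis plan that follows 9.7 literally would contain adjusted rates of SADRs and ADRs and no model for SAEs or HOIs. The SADR rate would then be open to being read as the serious-event rate. It would also depend on a judgement that, for retrospective data, may be made long after the event; section 9.5 plans a retrospective timeframe of around 3 years. Section 9.7 itself expects retrospective and prospective collection to differ. Relatedness is one more item on which they could differ.

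**Working it through.** The documents give neither an SAE rate nor the share of SAEs judged related, so this is mainly a comparison of text.

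**1. Promised against modelled outcomes**

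| Place | SAEs | HOIs | ADRs, SADRs | AESIs |
|---|---|---|---|---|
| Section 8 and synopsis, objective | yes, as rates | yes, as focus | no | no |
| 9.7, Poisson | no | no | yes | no |
| Synopsis, Poisson | no | no | yes | no |
| 9.7, Cox | not named | not named | yes | yes |
| Synopsis, Cox | not named | not named | yes | no |

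Both Cox sentences also mention time-to-event data in general, without naming an event.

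**2. Whether another sentence supplies the missing rate**
- The descriptive sentence in 9.7 gives numbers and percentages of patients with 95% confidence intervals. The glossary defines a rate as events over person-time, so these percentages are not rates.
- Annex 1, section 3, mentions crude and adjusted incidence rates but names no event type. For measures of occurrence it refers back to 9.7, which names only ADRs and SADRs.
- The Cox model gives time-to-event results, not rates per person-time.

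**3. Effect of the causality filter.** Let f be the share of SAEs judged related. Over the same person-time:

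SADR rate = f × SAE rate; shortfall relative to the SAE rate = 1 − f.

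The shortfall is zero only if f = 1. The documents do not give f, so no figure can be attached. The formula does not apply to ADRs: they include non-serious events and could outnumber SAEs.

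**4. Study size.** Section 9.5 rests on AE proportions with no causality condition. With n = 1.96² × p(1 − p) / d², and 95% two-sided assumed because 9.5 gives no level:
- p = 3.2%, d = 0.02: 297.5, so 298
- p = 5.2%, d = 0.025: 303.0, so 303
- p = 7.6%, d = 0.03: 299.7, so 300

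The stated 300 is reproduced. The sizing basis is thus not causality-filtered either, and naming SAEs as outcomes changes no study-size figure.

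**5. What is collected (11.1, 11.3.1, 11.4)**
- All SAEs, whatever the cause. Serious HOIs are therefore covered.
- Non-serious events judged related, as ADRs.
- Non-serious events judged unrelated, if they led to dose modification, interruption or discontinuation.
- Other non-serious events judged unrelated: not collected.
- Laboratory abnormalities that need intervention or change dosing: recorded if also considered causally associated. Those with signs or symptoms are recorded if they meet the AE or SAE definition. This bears on transaminase elevation and neutropenia. ALT, AST and neutrophil counts are collected separately when available (9.3).

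SAE rates regardless of causality can therefore be computed from the planned data. HOI rates regardless of causality can be computed in full only for serious HOIs.

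**The case against.** The best defence is that 9.7 never says only. The commitment to SAE rates stands in section 8, Annex 1 speaks of crude as well as adjusted rates, and the synopsis attaches the word adjusted to ADRs and SADRs. On that reading, crude SAE and HOI rates are intended, regression is an addition for reactions, and the detailed event list belongs in the analysis plan. AESIs would simply be the HOIs under another name.

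Part of this stands. A reader might infer that the study's main estimates will all be causality-filtered. The protocol does not rank the Poisson model as main, and crude SAE rates remain possible under section 8. The descriptive percentages and the general time-to-event wording carry no causality filter.

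A reader might also infer that both modelled rates fall below the SAE rate, or that events in advanced lymphoma will readily be put down to the disease. The first is true only of SADRs. The second overlooks section 11.5: a no requires evidence of another cause, and for SAEs an alternative must be given, whereas a yes needs only a reasonable possibility. That rule leans towards related.

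What does not stand is that the gap is a detail for the analysis plan. The protocol chose its modelled outcomes, twice, and left out those of its own objective. No sentence ties crude rates to SAEs, and none links AESIs to the HOIs.

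**Conclusion.** The mismatch is real and lies within the protocol. The objective calls for rates of SAEs with a focus on HOIs, and the only named rate model covers ADRs and SADRs, which depend on investigator-judged causality. An SADR rate understates the SAE rate by the share judged unrelated. The documents do not give that share, and nothing in them supports a numerical estimate. The understatement does not apply to ADRs. AESIs is an undefined term used once, in 9.7, where the defined set is the HOIs; by itself that is a matter of terminology.

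No SAE data are lost, because all SAEs are collected. The defect is therefore in the analysis text and can be put right there. For HOIs the limit is partly one of collection, so complete all-cause HOI rates cannot be promised. The conclusion rests on reading the outcome lists in 9.7 and the synopsis as written.

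**What to change.** In section 9.7 and the synopsis:
- Name all SAEs, regardless of causality, as outcomes of the crude rate (per person-time, with 95% CI), the Poisson model and the time-to-event analyses. Keep ADRs and SADRs as additional outcomes.
- Replace AESIs by HOIs in 9.7 and add HOIs to the matching synopsis sentence, referring to the list in 9.3.
- Report HOI rates regardless of causality for the events that 11.1 and 11.4 capture, which means serious HOIs in full. State that non-serious HOIs judged unrelated and without a dose change are not fully captured.
- For transaminase elevation and neutropenia, use the collected laboratory values where available.

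The cost is protocol wording and a few more tables. The SAE part needs no new data, and the study size is unaffected.

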Rate	A measure of event occurrence, calculated by dividing the total number of events by the total amount of person-time within an exposure category
Risk	The proportion of a fixed cohort in which an outcome occurs during a specified period of time
Start of data collection	Date from which information on the first study subject is first recorded in the study dataset

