### **9.5. Study Size**

This study aims to include patients who have been or are currently being treated with idelalisib according to the product information and treatment guidelines for the treatment of refractory FL after marketing authorization in the EU (September 2014) and Australia (January 2015).

Prevalence data for iNHL in the EU are limited. HAEMACARE, a European cancer registry-based project on hematologic malignancies funded by the European Commission, provides European incidence rates but not prevalence data {Sant 2010}. Australian prevalence data could not be identified. The Decision Resources Group (<http://www.decisionresourcesgateway.com/index.aspx>) estimated a 10-year limited-duration prevalence for FL in 5 major EU countries (France, Germany, Italy, Spain, and United Kingdom) over the 2011-2021 forecast period based on cancer registry databases in the EU-5. The EU prevalence estimates for FL ranged from 1.4 (Spain) in 2011 to 3.1 (France) per 10,000 in 2015 (RMP, section 1.1.1.4.2).

Based on the pivotal studies 101-09, GS-US-313-0124 and GS-US-313-0125 the median treatment period is estimated to be 8 months, taking into account that studies GS-US-313-0124 and GS-US-313-0125 were terminated early. Thus, a retrospective timeframe of around 3 years and a prospective observation period of another 2.5 years allow data of approximately 300 patient-years to be collected.

A sample size of 300 patient-years is based on the chance to find a proportion of adverse events of 3.2% with a precision of 2%. The table below shows the relationship between various detectable single proportions of AEs and precision of the estimate.

Proportions found in studies 101-09, GS-US-313-0124 and GS-US-313-0125 were 1.4% ( Grade 3 diarrhea and/or colitis), 2.0% (( Grade 3 febrile neutropenia), 6.1% (( Grade 3 infection) and 8.1% (( Grade 3 rash).

Proportion of AEs	3.2%	5.2%	7.6%
Precision	0.02	0.025	0.03

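### The Poisson model for ADR and SADR rates makes no allowance for variation between patients; if all events are counted and are frequent, ordinary Poisson intervals would be too narrow

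*Protocol*

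**What the plan says.** Section 9.7 gives one model for the rates: "Multivariate Poisson regression analyses will be used to estimate rates of ADRs and SADR". The covariates are demographics, baseline disease assessment, medical history, treatment history and treatment changes. The synopsis says the same: "Multivariate Poisson regression analyses will be used to estimate adjusted rates of ADRs and SADR".

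The counting rule comes from the glossary in Section 2, which defines a rate as "A measure of event occurrence, calculated by dividing the total number of events by the total amount of person-time within an exposure category". Risk has its own entry there, as the proportion of a fixed cohort in which an outcome occurs. Read together, these make the numerator of a rate all events, repeats included.

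Section 9.7 mentions 95% confidence intervals only for the "number and percentage of patients in each categorical definition including 95% confidence intervals". It states no interval, offset or variance estimator for the Poisson rates. The protocol nowhere mentions overdispersion, robust or clustered standard errors, or a negative binomial model.

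**The concern.** Ordinary Poisson standard errors take the variance of a count to equal its mean. That fails when some patients are more prone to events than others and the covariates do not capture the difference. ADRs are a broad class here: Section 11.3.4 sets no severity threshold, and Section 11.1 collects them from prescription until 6 months after the end of treatment. One patient can therefore contribute several, and susceptibility may well differ from patient to patient.

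The precision of the rates is at stake. The study tests no hypothesis, its size rests on precision (Section 9.5), and the checklist in Annex 1 describes crude and adjusted incidence rates as what will be calculated. Intervals that are too narrow would overstate how well the ADR and SADR rates are known.

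**Working it through.** **The plan's own figure.** Section 9.5 says: "300 patient-years is based on the chance to find a proportion of adverse events of 3.2% with a precision of 2" percent. With n = 1.96² × p(1 − p) / d², the three table pairs give:
- 3.2% and 0.02: 297.5, so 298
- 5.2% and 0.025: 303
- 7.6% and 0.03: 299.7, so 300

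The 300 is reproduced, by a formula for a binomial proportion in which each patient counts once. It therefore contains no allowance for overdispersed event counts. (That it comes out as a number of patients, not patient-years, is a separate matter.)

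**Inputs from the protocol.** Median treatment 8 months (9.5); observation until 6 months after discontinuation (9.1); about 300 patient-years (9.5). Section 9.5 also gives event proportions for four outcomes: "Proportions found in studies 101-09, GS-US-313-0124 and GS-US-313-0125 were 1.4" percent for the lowest, then 2.0%, 6.1% and 8.1%.

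**Assumed, because the protocol gives no figure.** Mean events per patient μ = 0.5, 1 or 2; gamma frailty with mean 1 and variance k = 0.5 or 1 (variation in risk left after adjustment).

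**Formula.** Let patient i, followed for time T, have a Poisson count with mean λuT, where u is the frailty. The variance of the total count divided by its Poisson variance is

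φ = 1 + kμ(1 + c²),

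where c is the coefficient of variation of follow-up. The correct standard error is √φ times the Poisson one, and the actual coverage of a nominal 95% interval is 2Φ(1.96/√φ) − 1.

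**Follow-up.** Two cases:
- Equal follow-up: c² = 0.
- Exponential treatment time (assumed) with median 8 months: mean 8/ln 2 = 11.54 months. Adding 6 gives 17.54 months, or 1.46 years, and c² = (11.54/17.54)² = 0.433. Then 300/1.46 is about 205 patients.

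| μ | k | φ, equal | Coverage | φ, unequal | Coverage | Simulated, unequal |
|---|---|---|---|---|---|---|
| 0.5 | 0.5 | 1.25 | 92.0% | 1.36 | 90.7% | 91.7% |
| 0.5 | 1 | 1.50 | 89.0% | 1.72 | 86.5% | 87.2% |
| 1 | 0.5 | 1.50 | 89.0% | 1.72 | 86.5% | 86.7% |
| 1 | 1 | 2.00 | 83.4% | 2.43 | 79.1% | 79.8% |
| 2 | 0.5 | 2.00 | 83.4% | 2.43 | 79.1% | 79.7% |
| 2 | 1 | 3.00 | 74.2% | 3.87 | 68.1% | 68.8% |

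The last column is from 4,000 simulated datasets of 205 patients per row, with no covariates in the model. In the same datasets, patient-level robust standard errors gave 94.0% to 95.2% coverage.

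**Repeats without heterogeneity.** With k = 0 and the same μ, ordinary Poisson intervals covered 94.3% to 95.1%, although repeat events were counted.

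**Rare single outcomes.** Treat 3.2% and 8.1% as rates of 0.032 and 0.081 per patient-year. Simulated with equal follow-up (450 patients for 8 months, or 257 for 14 months) and k = 0.5 or 1, φ is 1.01 to 1.10 and ordinary coverage is 93.6% to 96.2%. The worst case in the unequal follow-up formula is λ = 0.081 with k = 1: μ = 0.081 × 1.46 = 0.118, φ = 1 + 0.118 × 1.433 = 1.17, coverage 93.0%.

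**The case against.** The strongest reply is that Section 9.7 names a model and says nothing on standard errors. Poisson regression with sandwich errors is still Poisson regression and would comply with the text as written, and such detail is often left to the SAP, which is not at hand. This stands in part. A reader might infer that the reported intervals will be too narrow, but the protocol specifies no interval for the rates, so only a conditional statement is supported.

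A reader might also infer that counting repeat events is itself the fault. It is not: without unexplained differences in risk between patients, coverage stays near 95%.

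The all-events reading rests on a general glossary entry, not on Section 9.7. That is a fair caution, but the entry is the protocol's only definition of a rate.

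The simulation has no covariates, and the planned adjustment would absorb some heterogeneity. This is also fair. The assumed frailty variance must be read as what remains after adjustment, and the protocol offers nothing to fix its value.

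Finally, a reader might infer that chance differences between retrospective and prospective strata would be declared real. The protocol plans stratified analyses but no test between strata, and Annex 1 says that no comparisons will be made. That stronger consequence is not supported.

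What remains is that the protocol chose the model and defined the numerator, but made no provision for the usual way in which that pairing fails.

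**Conclusion.** The point holds in conditional form. If all ADRs or SADRs are counted, occur at 0.5 to 2 per patient, and vary between patients with residual frailty variance 0.5 to 1, ordinary model-based Poisson 95% intervals would cover roughly 92% down to 70%. The correct standard error would be about 1.1 to 2.0 times the Poisson one (√1.25 = 1.12 to √3.87 = 1.97). Event frequency and frailty variance are both assumptions; the protocol gives neither. For single rare outcomes at the proportions in Section 9.5 the effect is negligible: about two points of coverage at most over the same frailty range. The point therefore concerns the aggregate ADR and SADR rates. It is worth acting on because those rates are a main output and the remedy is nearly free.

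**What to change.** Add one sentence to Section 9.7, mirrored in the synopsis: all-event ADR and SADR rates are estimated by Poisson regression with a log person-time offset and patient-level robust (sandwich) standard errors, or by negative binomial regression.

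This needs no new data and no change to collection. If dispersion turns out to be 1, almost nothing is lost; if counts are overdispersed, the intervals become somewhat wider, as they should. Reporting a first-event rate alongside is optional and not part of the correction.
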